9.5.1.5.2 SERIOUS ADVERSE EVENTS AND EVENTS ASSOCIATED WITH SPECIAL SITUATIONS

A serious adverse event (SAE) is any untoward medical occurrence that at any dose:

- Results in death
- Is life-threatening (ie, the subject was at an immediate risk of death from the adverse event as it occurred; this does not include an event that, had it occurred in a more severe form or was allowed to continue, might have caused death)
- Requires inpatient hospitalization or prolongation of existing hospitalization
- Results in persistent or significant disability/incapacity

- Is a congenital anomaly/birth defect (in the child of a subject who was exposed to the study drug)

Other important medical events that may not be immediately life-threatening or result in death or hospitalization but, when based on appropriate medical judgment, may jeopardize the subject or may require intervention to prevent one of the outcomes in the definition of SAE listed above should also be considered SAEs. Medical and scientific judgment should be exercised in deciding whether expedited reporting is appropriate in such situations.

In addition to the above, other events associated with special situations include: pregnancy or exposure to the study drug through breastfeeding; AEs associated with study drug overdose, misuse, abuse, and medication errors (See Sections 9.5.4.2 and 9.5.4.3). These events associated with special situations are to be captured using the SAE procedures but are to be considered as SAEs only if they meet one of the above criteria. All AEs associated with special situations are to be reported on the CRF whether or not they meet the criteria for SAEs.

All SAEs must be followed to resolution or, if resolution is unlikely, to stabilization.

The following hospitalizations are not considered to be SAEs because there is no “adverse event” (ie, there is no untoward medical occurrence) associated with the hospitalization:

- Hospitalizations for respite care
- Planned hospitalizations required by the protocol
- Hospitalization planned before informed consent (where the condition requiring the hospitalization has not changed post study drug administration)
- Hospitalization for administration of the study drug or insertion of access for administration of the study drug
- Hospitalization for routine maintenance of a device (eg, battery replacement) that was in place before study entry

9.5.1.5.3 STUDY-SPECIFIC ADVERSE EVENTS

In a non-clinical toxicity study of sodium sulphobutylether-beta-cyclodextrin (hereinafter “SBECD”), which is one of the additives in this study drug, vacuolation was observed in tubular epithelial cells, suggesting that patients with impaired renal function have a risk of SBECD accumulation (Luke, et al., 2010). In addition, there have been reports of anaphylaxis, possibly due to SBECD, with other formulations containing SBECD.

In this study, based on the above findings, adverse events associated with renal dysfunction, and adverse events associated with anaphylaxis will be handled as “adverse events of special interest (AESIs)” and recorded in the CRF.

For the procedures for reporting adverse events of special interest, see Section 9.5.4.3.2

1. Adverse Events Associated With Renal Dysfunction

If an adverse event associated with renal dysfunction occurs, and does not resolve at the time point when the Follow-up Phase is completed, the investigator will monitor the subject for 14 days from the follow-up visit, regardless of severity, and will continue following up the subject as needed until resolution of the event or, if resolution is unlikely, until stabilization of the symptom or sign. During this period, the subject will be followed up continuously by renal function monitoring at unscheduled visits (eg, once weekly, or at a frequency deemed necessary by the investigator).

2. Adverse Events Associated With Anaphylaxis

In the event of an adverse event associated with anaphylaxis, the investigator will take the following responsive actions:

- Take the first response, for example, by immediately referring the subject to an appropriate clinical department;
- Make a decision regarding whether or not to continue administration of the study drug to the subject, based on advice from the physician in the above-mentioned department;
- In the event of an adverse event associated with anaphylaxis while continuing intravenous administration of the study drug, discontinue the administration. In the event of any symptom or sign that is suspected of anaphylaxis while continuing intravenous administration of the study drug, careful judgment will be exercised in determining whether or not to continue the administration.

The follow-up of anaphylaxis will be continued until resolution of the event or, if resolution is unlikely, until stabilization of the symptom or sign.

9.5.1.5.4 LABORATORY MEASUREMENTS

The clinical laboratory tests to be performed, including hematology, chemistry, and urinalysis, are summarized in Table 1. The Schedule of Procedures/Assessments (Table 2) shows the visits and time points at which blood for clinical laboratory tests and urine for urinalysis will be collected in the study. The sampling date will be recorded in the CRF.

Table 1 Clinical Laboratory Tests

Category	Parameters
Hematology	Hematocrit, hemoglobin, platelets, RBC count, and WBC count with differential (basophils, eosinophils, lymphocytes, monocytes, neutrophils)
Chemistry	
Electrolytes	Sodium, potassium, chloride, calcium
Liver function tests	Alanine aminotransferase, aspartate aminotransferase, alkaline phosphatase, gamma glutamyl transpeptidase, total bilirubin
Renal function tests	Blood urea/blood urea nitrogen, creatinine
Other	Albumin, cholesterol, glucose, lactate dehydrogenase, phosphorus, total protein, triglycerides, uric acid
Urinalysis	glucose, ketones, occult blood, pH, protein, specific gravity

RBC = red blood cell, WBC = white blood cell

The clinical laboratory tests indicated above will be performed by the central laboratory.

A laboratory abnormality may meet the criteria to qualify as an AE as described in this protocol (see Section 9.5.1.5.1). In these instances, the AE corresponding to the laboratory abnormality will be recorded on the Adverse Event CRF.

9.5.1.5.5 VITAL SIGNS AND WEIGHT MEASUREMENTS

Vital sign measurements (ie, systolic and diastolic blood pressure [BP] [mmHg], pulse [beats per minute], respiratory rate [per minute], and body temperature [in centigrade]), and weight (kg) will be recorded on the CRF at the visits designated in the Schedule of Procedures/Assessments (Table 2) by a validated method. Blood pressure and pulse will be measured after the subject has been resting for 5 minutes. All BP measurements should be performed on the same arm, and preferably by the same person.

9.5.1.5.6 PHYSICAL EXAMINATIONS

Physical examinations will be performed as designated in the Schedule of Procedures/Assessments (Table 2). Documentation of the physical examination will be included in the source documentation at the site. Only changes from the screening physical examination findings that meet the definition of an AE will be recorded on the Adverse Events CRF.

9.5.1.5.7 ELECTROCARDIOGRAMS

Twelve-lead electrocardiograms will be obtained as designated in the Schedule of Procedures/Assessments (Table 2) after the subject has been resting for 5 minutes. The

investigator will record the presence or absence of any ECG abnormalities (Normal/Abnormal, Not Clinically Significant/Abnormal Clinically Significant) based on the relevant ECG findings in the CRF.

In the Pretreatment Phase, only if the QTcF interval is more than 450 ms, an additional 2 consecutive ECGs separated by 5 or more minutes will be recorded.

An ECG abnormality may meet the criteria of an AE as described in this protocol (see Section 9.5.1.5.1). In these instances, the AE corresponding to the ECG abnormality will be recorded on the Adverse Events CRF.

9.5.1.5.8 OTHER SAFETY ASSESSMENTS

Not applicable.

9.5.1.6 Other Assessments

9.5.1.6.1 PREGNANCY TEST

At Visit 1, all females of childbearing potential will undergo the serum β -hCG pregnancy test (the measurements will be performed by the central laboratory). At Visit 2 and thereafter, all females of childbearing potential will undergo the urine β -hCG pregnancy test (the measurements will be performed by each investigational site).

9.5.2 Schedule of Procedures/Assessments

9.5.2.1 Schedule of Procedures/Assessments

Table 2 presents the schedule of procedures/assessments.

Table 2 Schedule of Procedures / Assessments in Study E2007-J081-240

Phase	Pretreatment Phase		Treatment Phase ^a				Follow-up Phase ^{b, c}	Unscheduled Visit ^k	Early Discontinuation Visit
	Day -28 to -7 (Screening)	Day -1	Day 1	Day 2	Day 3	Day 4			
Study Day(s) (from Day 1 of Treatment Phase)							7 days after the last intravenous infusion		
Visit	1	2	3a	3b	3c	3d		4	
Procedure/Assessment									
Informed consent/assent ^d	X								
Inclusion/exclusion criteria	X	X	X						
Physical examinations	X	X	X ^m	X ^m	X ^m	X ^m	X	X	X
Medical history	X								
Concomitant medications/therapies	X ^e	X ^e	X ^e	X	X	X	X	X	X
Hospitalization		X	X	X	X	X ^l			
Intravenous administration of the study drug (intravenous infusion of perampanel)			X	X ⁿ	X ⁿ	X ⁿ			
Oral perampanel administration at the hospital		X ⁿ							
Adverse events ^f	X	X	X	X	X	X	X	X	X
Oral perampanel/study drug compliance	X	X	X	X	X	X	X		X
Dispense subject diary	X		X			X			X
Return and review subject diary			X			X	X ^o		X
Discontinuation/continuation judgment ^g		X	X	X	X	X			
Vital signs and weight/height ^h	X	X	X ^m	X ^m	X ^m	X ^m	X	X	X
Clinical laboratory evaluations	X	X				X ^m	X	X	X
PK blood sampling for perampanel ⁱ		X	X	X	X	X			
Urine drug screen	X								
Urine pregnancy test ^j		X					X	X	X
Serum pregnancy test ^j	X							X	
12-lead ECG	X	X				X ^m	X	X	X

- a: The date of each visit to be specified based on the date of Visit 3a. The Treatment Phase is defined as the period beginning at the start of the study treatment (intravenous infusion of perampanel) on Day 1 to immediately before the oral perampanel administration on Day 5.
- b: Visit to be performed within +7 days of the schedule. The visit is to be specified based on the date of the last intravenous infusion of perampanel.
- c: To be completed by subjects who received at least 1 intravenous infusion of perampanel, in principle.
- d: Informed consent must be obtained before any study-related procedure.
- e: Prior and concomitant medication(s)/therapies(s).
- f: Adverse events will be collected from the time the subject signs the informed consent form through the 21 days after the subject's last intravenous infusion of perampanel. Serious adverse events will be collected for 28 days after the subject's last intravenous infusion of perampanel.
- g: During the period from Visit 3a to Visit 3d, if a subject experiences seizures or has safety issue, the investigator will make as judgment regarding study continuation/discontinuation based on the subject's tolerability and efficacy.
- h: Height is to be measured only at Visit 1.
- i: Blood samples for the plasma perampanel concentration will be collected at predose and at 0.5, 1, and 1.5 hours after the oral administration of perampanel on Visit 2 (Day -1), predose and at 0.5 hours after the start of intravenous infusions of perampanel on Visits 3a, 3b, 3c, and 3d (Days 1, 2, 3, and 4). In addition, for the blood samplings at 0.5 hours after the start of intravenous infusions of perampanel on Days 1 through 4, they should be performed immediately after completion of the intravenous perampanel infusions (ie, within 5 minutes after completion).
- j: All females of childbearing potential will undergo the serum β -hCG pregnancy test at Visit 1. At Visit 2 and thereafter, all females of childbearing potential will undergo the urine β -hCG pregnancy test.
- k: At an Unscheduled Visit, only the procedures/assessments that the investigator has judged as necessary according to the subject's condition will be performed.
- l: Subjects will be discharged from the hospital the next day following Day 4 (ie, on Day 5).
- m: The examinations will be conducted predose.
- n: The start time of intravenous infusions of perampanel from Day 1 to Day 4 will be designated as the same time as the administration time of oral perampanel on Day -1 (allowance window: ± 1 hour).
- o: As for subjects who have been withdrawn from the study, recording in the diary after discontinuation will continue as far as possible. Further, the investigator or the designated investigator's staff should record seizure counts and types on the CRF for up to 14 days after the subject's last intravenous infusion of perampanel.

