9.1.2 Treatment Phase

The Treatment Phase is defined as the period beginning at the start of intravenous infusion of perampanel on Day 1 to immediately before the oral perampanel administration on Day 5.

Hospitalized subjects will be switched from oral perampanel on Day 1 to intravenous infusion of perampanel at a dose equivalent to the oral perampanel dose. Subjects will receive 30-minute intravenous infusions of perampanel once a day for 4 days under inpatient conditions (Days 1 through 4).

Subjects will be discharged from the hospital the day after the last intravenous infusion of perampanel (ie, Day 5), and treatment must be switched back to their original dose of oral perampanel.

If subjects cannot continue intravenous infusion of perampanel for any reason(s), they must discontinue the study.

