9.1.3 Follow-up Phase

The Follow-up Phase is defined as the period after switching back to oral perampanel administration.

The assessments at the Follow-up Visit will be conducted 7 days (allowance window: +7 days) after the last intravenous infusion of perampanel.

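### For a subject who completes treatment, the only scheduled Treatment Phase laboratory sample precedes the fourth infusion, and the next follows 7 to 14 days after it

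*Protocol*

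**What the plan says.** - **Laboratory schedule (protocol 9.5.2.1, Table 2).** The row "Clinical laboratory evaluations" is marked at screening, Day -1, Day 4, Follow-up, Unscheduled and Early Discontinuation. Days 1, 2 and 3 are blank, and there is no Day 5 column.
- **Timing on Day 4 (Table 2, footnote m).** "The examinations will be conducted predose"
- **Dosing days (9.1.2).** There is one infusion on each of Days 1 to 4. The Treatment Phase ends just before the oral dose on Day 5.
- **Discharge (Table 2, footnote l).** Subjects leave hospital on Day 5.
- **Follow-up (9.1.3).** "The assessments at the Follow-up Visit will be conducted 7 days (allowance window: +7 days) after the last intravenous infusion of perampanel"
- **Renal safety (9.5.1.5.3).** A toxicity study of the excipient SBECD is cited as "suggesting that patients with impaired renal function have a risk of SBECD accumulation". On that basis "adverse events associated with renal dysfunction, and adverse events associated with anaphylaxis will be handled as" adverse events of special interest (AESIs).
- **Use of laboratory values.** Section 9.5.4.3.2 sends a renal AESI for expedited reporting if creatinine exceeds 3 times the upper limit of normal. Section 9.7.1.8.3 counts treatment-emergent markedly abnormal laboratory values (TEMAVs) from postbaseline results. BUN and creatinine are both in the panel (9.5.1.5.4, Table 1).

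**The concern.** The primary objective is the safety and tolerability of the switch to infusion, and section 9.2 defends four days as a length of treatment that allows safety to be judged. The protocol also names a renal hazard from the excipient and makes part of its reporting depend on creatinine. Yet no laboratory value is scheduled soon after the complete course. The on-treatment laboratory summaries would describe subjects after three infusions, and the only scheduled value after all four comes at least a week later.

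What is at stake is narrow. A change in creatinine, or in any other laboratory value, that follows the fourth infusion, causes no symptoms and settles before the Follow-up Visit would not appear in the by-visit tables, the shift tables or the TEMAV counts.

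**Working it through.** The protocol gives no figure to reproduce here, and the 20 subjects are stated to be a feasibility number (9.7.2). The check is a count and day arithmetic for a subject who receives all four infusions.

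**Inputs.** Infusions on Days 1, 2, 3 and 4 (9.1.2). Laboratory sample on Day 4, before dosing (Table 2, footnote m). Infusion start times within 1 hour either side of the Day -1 oral dosing time (9.4.1; Table 2, footnote n). Follow-up at last infusion + 7 days, window + 7 days (9.1.3; Table 2, footnote b).

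**Step 1: infusions before the on-treatment sample.** Days 1, 2 and 3 come before it, so 3 of 4 = 75%.

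**Step 2: distance from the third infusion.** Start to start is nominally 24 hours. With each start allowed to vary by 1 hour, the range is 24 - 2 = 22 to 24 + 2 = 26 hours. A sample taken immediately before the Day 4 infusion is therefore about one day after infusion 3.

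**Step 3: gap after the fourth infusion.** Earliest Follow-up: Day 4 + 7 = Day 11. Latest: Day 4 + 14 = Day 18. The gap without a scheduled value is 7 to 14 days.

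| Scheduled sample | Infusions received | Time since last infusion |
|---|---|---|
| Screening, Day -1 | 0 | none given |
| Day 4, predose | 3 | 22 to 26 hours from start of infusion 3 |
| Day 5 | 4 | no sample scheduled |
| Follow-up, Day 11 to 18 | 4 | 7 to 14 days |

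**Step 4: what the tables can detect.** A completer has two scheduled values after the first infusion. By Appendix 1, creatinine grade 2 starts above 1.5 times the upper limit of normal, and 9.7.1.8.3 counts a rise from baseline to grade 2 or higher as a TEMAV. A rise past that line after infusion 4 that has reversed by Day 11 falls between the two values and is not counted, unless an unscheduled test catches it.

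**Step 5: other routes to a laboratory value.** Unscheduled tests are done only where the investigator judges them necessary (footnote k). Early Discontinuation tests apply only to subjects who stop (9.5.5). The extra renal monitoring in 9.5.1.5.3 applies to a renal event that has already been identified and is unresolved when the Follow-up Phase ends. None of these gives a routine value after infusion 4 in a completer.

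**The case against.** Several points on the other side are sound and limit the claim.

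- **The renal AESI is not left unchecked.** A reader might infer that renal safety is looked at after three doses and then dropped. The documents do not support that. AESIs are adverse events, and these are collected through 21 days after the last infusion and serious ones through 28 days (9.5.1.5.1; Table 2, footnote f). Unscheduled tests are allowed. Only a change that nothing else prompts anyone to look for is missed.
- **The mechanism is narrower than dose accumulation in everyone.** Section 9.5.1.5.3 ties accumulation to impaired renal function. Exclusion criteria 8 and 9 address clinically significant renal disease, subject to the investigator's opinion, and clinically significant abnormal laboratory values. The protocol gives no SBECD dose, half-life or creatinine time course, so it cannot be said that any renal effect peaks after the fourth infusion.
- **The missing quarter is not a quarter of new perampanel exposure.** Subjects have taken a stable equivalent oral dose for at least 28 days and return to it on Day 5. One in four is a count of infusions of the new formulation. It does not measure lost detection.
- **Predose timing may have a purpose.** It could inform the decision to give the fourth infusion. Footnote g refers to safety issues generally and does not exclude laboratory findings. However, no dosing rule names the Day 4 result, and section 9.5.1.5.4 states: "The clinical laboratory tests indicated above will be performed by the central laboratory". Turnaround is not given, so whether a result would be back before the infusion is unknown. The conclusion does not depend on it.
- **Nothing fails to compute.** The laboratory tables can be produced, and the Follow-up sample does come after all four infusions.

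What stands is that no scheduled laboratory value lies close to the end of the full course, although the subject is in hospital when one could be taken.

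**Conclusion.** The point holds as a low-cost improvement to the schedule. For completers, the one scheduled Treatment Phase laboratory sample follows 3 of 4 infusions, and the next comes 7 to 14 days after the fourth. The consequence is confined to transient, symptomless laboratory changes after the full course, creatinine among them. The protocol gives no basis for estimating how often these would occur.

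The conclusion assumes that the subject receives all four infusions on schedule and has no unscheduled test. A reader might take the schedule to contradict the AESI section. It does not: section 9.5.1.5.3 promises no laboratory test at any particular time after the last infusion.

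**What to change.** In Table 2, add a Day 5 column for the time before discharge and before the oral perampanel dose. This is still inside the Treatment Phase as 9.1.2 defines it. Move the Day 4 predose laboratory sample (hematology, chemistry, urinalysis) to that column, and name it in 9.7.1.8.3 as the end-of-treatment laboratory value. Footnote m stays for the other Day 4 assessments.

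In 9.5.5, make clear that a subject who stops on Day 4 before the infusion still has the Early Discontinuation laboratory tests, since the Day 4 draw could no longer stand in for them.

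**Cost.** The number of laboratory samples per subject is unchanged and the subject is already an inpatient. The value after three infusions is lost. One venipuncture per subject is probably added, about 20 in all for 20 subjects, because the Day 4 laboratory draw could be shared with the predose PK sample (footnote i) and no PK sample is scheduled on Day 5. If the sponsor wants to keep the value after three infusions, the alternative is to retain Day 4 and add Day 5, at one extra laboratory sample per subject.

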9.5.3 Appropriateness of Measurements

The safety assessments in this study are standard evaluations to ensure subject safety.

The efficacy assessment (ie, seizure counts and types) comprises standard measurements commonly used in studies evaluating the effect of AEDs.

9.5.4 Reporting of Serious Adverse Events, Pregnancy, and Events Associated With Special Situations

9.5.4.1 Reporting of Serious Adverse Events

All SERIOUS ADVERSE EVENTS, regardless of their relationship to study treatment, must be reported on a completed SAE form as soon as possible but no later than 1 business day from the date the investigator becomes aware of the event.

Serious adverse events, regardless of causality assessment, must be collected through the last visit and for 28 days after the subject's last dose of study drug. All SAEs must be followed to resolution or, if resolution is unlikely, to stabilization. Any SAE judged by the investigator to be related to the study treatment or any protocol-required procedure should be reported to the sponsor regardless of the length of time that has passed since study completion.

The detailed contact information for reporting of SAEs is provided in Attachment 1.

It is very important that the SAE report form be filled out as completely as possible at the time of the initial report. This includes the investigator's assessment of causality.

Any follow-up information received on SAEs should be forwarded within 1 business day of its receipt. If the follow-up information changes the investigator's assessment of causality, this should also be noted on the follow-up SAE form.

Preliminary SAE reports should be followed as soon as possible by detailed descriptions including copies of hospital case reports, autopsy reports, and other documents requested by the sponsor.

